The Telehealth Exercise and Mindfulness for Pain in Osteoarthritis (TEMPO) is a longitudinal, parallel arm, 14-week clinical trial that will investigate the feasibility of an 8-week telehealth-delivered, group-based mindful exercise program. For this, forty people with knee OA will be recruited. These participants will be randomly assigned to either an 8-week mindful exercise program OR an 8-week exercise only program. Both programs will include weekly sessions (n=8 total) that will be delivered in a group setting (n=10 per group) by real-time videoconferencing (HIPAA-protected Zoom). Before the start of the interventions, all participants will attend an individualized remote randomization and telehealth training session where participant's group assignment will be randomized, and instructions for home set up and requirements for the remote sessions will be discussed. Participants will be administered surveys on pain, function, and mood before the start of the intervention (week 0), at post-intervention (week 8), and 6-weeks after the end of the interventions (week-14). Participants will be given an option to participate in two in-person visits at Boston University before the start (baseline visit) and at the end of the interventions (post-intervention visit). During these optional in-person visits, the participant's function, muscle strength, sensitivity to painful stimulus, and brain activity will be collected. Brain activity will be measured using functional near-infrared spectroscopy (fNIRS). At the end of the 8-week interventions, participants in the mindful exercise group will be invited to participate in individual interviews. The interviews will be conducted over Zoom to understand participant's perspective related to acceptability of the mindful exercise intervention

2b. Schedule of Visits

Figure 1 is a schematic diagram depicting the study flow. A list of measurements collected at each visit is shown below in **Table 1**. Apart from the research and intervention visits, the various timepoints of email and telephone contact with the participants in the study is shown in **Table 2**.

[figure not shown]

Figure 1. Study flow for participants in the study

 Table 1. Schedule of Study Visits and Measurements

Week	~ -3	-2	-1	0	1	2	3	4	5	6	7	8	9-13	14
Visits			BV-R	RTT								W8-R		W14-R
Telephone Screening	X													
Consent and Enrollment	X													
Randomization				X										
Exercise Program					X	X	X	X	X	X	X	X		

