- Seminars and recruitment sessions at senior centers, churches, and other sites where older adults gather
- Mass mailing: Mass mailing will be considered if additional recruitment strategies are needed to meet accrual
 goals

3b. Eligibility Criteria

Inclusion Criteria

- Meet National Institute for Health and Clinical Excellence clinical guidelines for knee osteoarthritis (i.e., age ≥ 50 years, presence of activity related pain, presence of morning knee stiffness ≤ 30 minutes)
- BMI<40
- Knee pain on most days for 3 months or more
- Average overall knee pain severity of ≥ 4 on a 11-point numeric rating scale during previous week
- Able to attend remote sessions
- Can speak and understand English at a sufficient level to understand the study procedures and informed consent.
- Available for study duration

Exclusion Criteria

- Contraindications to exercise
- Other pain in lower back or legs that is greater than knee pain
- Received physical therapy treatment for knee OA in the past 6 months or currently receiving physical therapy
- Received any mindfulness programs such as Tai Chi, meditation, etc. in the past 6 months or currently receiving such program
- Currently receiving chemotherapy or radiation therapy for cancer except non-melanoma skin cancer
- History of other disease that may involve the index joint including inflammatory joint disease such as rheumatoid arthritis, seronegative spondyloarthropathy (eg, ankylosing spondylitis, psoriatic arthritis, inflammatory bowel disease related arthropathy), crystalline disease (eg, gout or pseudogout), lupus erythematosus, knee joint infections, Paget's disease affecting the knee, or knee joint tumors.
- Any knee surgery in the previous 6 months
- Joint replacement in either hip or ankle
- Previous knee osteotomy partial or total knee replacement in either knee
- Planned major treatment for knee OA (e.g., surgery, injections, physical therapy) during the study period
- Planned major surgery in the next 6 months
- Corticosteroid or hyaluronic acid injections in either knee in the previous 3 months
- Neurological conditions that impacts motor functioning (e.g., stroke, Parkinson's disease, Alzheimer's disease, Multiple Sclerosis, diabetic neuropathy, etc).
- Pregnancy (self-report)
- Participation in another clinical trial for any joint or muscle pain

- Suspected or known drugs or alcohol abuse
- Wrist fracture in both wrists within past 6 months (exclusion applies only to PPT testing)

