A randomization list will be generated by study biostatistician and will be stratified by sex. This provides an assignment that the study staff has no control over the randomization process and that each participant has an equal chance of being assigned to either group. These group assignments will be pre-specified and placed in sealed envelopes unmarked except for an envelope number (TEMPO1## or TEMPO2##) on the outside. Envelopes with numbers starting with the number 1 (e.g., TEMPO1##) will be for male participants and those starting with the number 2 TEMPO 2## will be for female participants. For participants who opted-in for the in-person baseline visit, the randomization procedures will occur inperson after the baseline data collection procedures have been completed.

Below is a script that the research assistant will use for the randomization procedures

4d. Post-Intervention (Week 8) Visit

The weekly attendance of the participants will be tracked on an Attendance Survey on REDCap. The completion of the 8th session will trigger the ASI for the post-intervention remote surveys. Participants will receive a total of 15 surveys, including self-reported pain, function, and psychological measures collected at baseline and feedback and satisfaction surveys. Those who opted in for the in-person baseline visit will be invited for the in-person post-intervention visit.

4e. Follow-up (Week 14) Surveys

Six weeks after the end of the 8-week intervention, participants will be administered six surveys related to their knee pain, function, perceived impression of change, and psychological measures.

4f. Weekly (Week 1-14) Surveys

All participants will be administered a short weekly survey starting from the start of the intervention (week 1) to the follow-up period (week 14). This weekly survey will include a question related to pain in a specific activity selected at baseline and will also include home exercise, physical activity, and medication log. For those assigned to the mindful exercise group, additional questions related to mindfulness and mindful exercise log will be included. The weekly survey will be administered by email using automated survey reminders in REDCap.

4g. Individual Interviews (Week 8)

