At the end of the 8-week interventions, participants from the mindful exercise intervention will be invited for individual interviews. The interviews will be conducted over Zoom by a professor who is an expert in qualitative methods and who was not involved in any other study procedures. The interview guide will be theoretically informed based on the Theoretical Framework of Acceptability(1). The interviews will be audio-recorded on Zoom and transcribed verbatim and de-identified by GMR transcription services in Boston.

5. Interventions Description, Overview, Objectives

5a. General Overview

Two days before the first intervention session, participants will receive a reminder email informing them of the date, time, and zoom link of the intervention session. This information will also be provided in the manual given to them at the baseline visit. One day before the intervention session, participants will receive a call from the research assistant reminding them of the first intervention session.

Participants in both groups will receive 8 telehealth, group-based, supervised intervention sessions. Participants in the exercise group will receive evidence-based strengthening and neuromuscular exercises for the knee for 12-weeks. Participants in the mindful exercise group will receive the same exercises but they will be trained on performing the exercises mindfully. The interventions will be conducted in two waves.

5b. Interventions

Interventions will be delivered in a group setting in two waves over 8-weeks. Once at least 12 people are recruited, interventions for wave 1 will commence. Recruitment and randomization processes will be ongoing while interventions for wave 1 participants are in progress. Once 40 participants are randomized, recruitment will cease and the interventions for the second wave of participants will commence.

[figure not shown]
Interventions in both mindful exercise and exercise groups will be delivered in a group setting via HIPAA-protected Zoom videoconferencing software. Along with the interventions below, participants in both groups will receive educational materials each week via email (Table 5), a program manual that contained information about study tasks and interventions, and a set of resistance bands and a step-up platform with adjustable height. After the end of the 8-week interventions, participants were asked to continue to practice on their own for another 6 weeks.

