Breath and counting meditation Training on how to use counting as an anchor				
	Session 3			
Moving meditation	Introducing how to combine movement and mindfulness			
Body scan meditation	Practice on how to use body sensation as an anchor			
Mindful exercises	Combining exercise and mindfulness			
Session 4				
Breath and counting meditation	Training on how to exercise using either the breath, counting,			
C	or body sensation as an anchor			
Walking meditation	Combining movement and mindfulness			

Mindful exercises	Combining exercise and mindfulness				
Session 5					
Awareness of breath meditation	Practice on how to use breath as an anchor				
Mindful exercises	Combining exercise and mindfulness				
	Session 6				
Awareness of breath meditation	Practice on how to use breath as an anchor				
Body scan meditation	Practice on how to use body sensation as an anchor				
Mindful exercises	Combining exercise and mindfulness				
	Session 7				
S.T.O.P meditation	Training on incorporating mindfulness in daily life				
(S=sit down, T=take a breath,					
O=observe, P=proceed with day)					
Pain-focused meditation	Training on how to detach from difficult sensations				
Mindful exercises	Combining exercise and mindfulness				
	Session 8				
Review and summary	A summary and practice of what was covered in the 8-week				
	program and practice of aware of breath and body scan				
	meditations				
Mindful exercises	Combining exercise and mindfulness				

7. Statistical Analysis Plan

The following outcome measures will be used to determine feasibility of the telehealth interventions in this study.

- a) Recruitment: Proportion of participants successfully contacted who agreed to participate in the study over 6-months
- b) Attendance: Proportion of sessions attended
- c) Retention: The percentage of participants who complete the post-intervention surveys at the end of the study period (12-weeks)

The number of safety events, and data for recruitment, attendance, and retention will be reported descriptively. Aggregate data for intervention adherence at home as well as feedback from the participants will be reported. For other PROs, within group changes and differences between groups along with 95% confidence intervals will be reported. Data will be reported using an intention-to-treat approach with data from all randomized participants included. Missing data will not imputed.

8. Safety Reporting

AEs, SAEs, and Unanticipated Problems Definitions

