Adverse event (AE) is any unfavorable or unintended diagnosis, sign (including abnormal laboratory finding), symptom, or diseases temporarily associated with the study intervention, which may or may not be related to the intervention. AEs include any new events not present during the pre-intervention period or events that were present during the pre-intervention period but have increased in severity.

Serious adverse event (SAE) is any AE that results in any of the following outcomes:

- Death,
- Life-threatening adverse experience,
- Inpatient hospitalization or prolongation of existing hospitalization,
- Persistent or significant disability/incapacity,
- Congenital anomaly/birth defect, or cancer, or any other experience that suggests a significant hazard, contraindication, side effect or precaution that may require medical or surgical intervention to prevent one of the outcomes listed above,
- Event that changes the risk/benefit ratio of the study.

An unanticipated problem is any incident, experience, or outcome that meets ALL of the following criteria:

- Unexpected in terms of nature, severity, and frequency, given the research procedures that are described in the protocol related documents the characteristics of the subject population being studied
- Related or possibly related to a subjects participation in the research study, and
- Suggests that the research places subjects or others at a greater risk of harm (including physical, psychological, economic, or social harm) related to the research than was previously known or recognized.

8a. Event Notification

The clinical tests used in this study offer minimal risks to participants and will be administered by an experienced team in working with this patient population. Participants will be asked if any events have occurred prior to each intervention or testing session and to report all activity-related symptoms of pain or discomfort to the investigator or research team member, who will decide if medical care is warranted, and arrange for that care as appropriate. Participants will be constantly supervised and assisted as necessary throughout their testing and training session.

Because this study's procedures pose relatively low risk to participants, weekly data and procedural reviews by the PI in consultation with study staff will be sufficient to identify and ameliorate any potential safety issues.

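### Safety is summarised only as a number of events; add the participants affected in each arm and a rule for counting recurrences

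*Combined protocol and SAP*

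**What the plan says.** Section 7 (Statistical Analysis Plan) contains a single sentence on safety: "The number of safety events, and data for recruitment, attendance, and retention will be reported descriptively". It names no count or percentage of participants with an event, no split by arm, seriousness or relatedness, and no rule for repeated events. The other measures in the section are better specified: recruitment and attendance are proportions, retention is a percentage, and patient-reported outcomes get between-group differences with 95% confidence intervals.

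Four other places bear on what that number will contain:

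- Section 8 (definitions) includes as AEs "events that were present during the pre-intervention period but have increased in severity".
- Section 3b (inclusion criteria) requires "Average overall knee pain severity of ≥ 4 on a 11-point numeric rating scale during previous week".
- Section 8a (Event Notification) says "Participants will be asked if any events have occurred prior to each intervention or testing session".
- Section 5a says "Participants in both groups will receive 8 telehealth, group-based, supervised intervention sessions".

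On size, the study overview says "forty people with knee OA will be recruited", and section 4c says of the randomisation that "each participant has an equal chance of being assigned to either group".

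Section 8a also has the AE form opened under the individual participant, with the principal investigator (PI) deciding attribution and severity.

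**The concern.** Everyone in this trial starts with a symptom that can worsen, worsening counts as an AE, and people are asked about events repeatedly. Several reports of much the same problem from one person are therefore foreseeable. A bare number of events gives each report equal weight, so the total may say more about one or two people than about the arm.

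Two things are at stake. First, the trial sets mindful exercise against exercise alone, so readers will look at safety by arm even without a test. With about 20 per arm, the arm with more events need not be the arm with more people affected. Second, the team planning the next trial will want the proportion of participants who have an AE, and an event total cannot supply it.

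**Working it through.** The documents state no AE rate, expected number of events or safety precision, so there is no safety figure to reproduce. The AE counts and rates below are assumptions chosen to show the range.

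**Inputs from the documents.** Total 40 (study overview). Equal chance of either arm (section 4c), so 40 / 2 = 20 per arm on average. This agrees with groups of 10 (study overview) in two waves (section 5a): 10 × 2 = 20 per arm, and 20 × 2 = 40. There are 8 intervention sessions per participant (section 5a).

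**Step 1: when do the two summaries disagree?** Let arm A have *a* participants with one event each. Let arm B have *b* < *a* participants with events, one of whom has *r* events and the rest one each. By participants, A is higher. By events, B is higher when (b − 1) + r > a, that is, when r ≥ a − b + 2.

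| Participants affected, A v B | Smallest r that reverses the totals |
|---|---|
| 4 v 3 | 4 − 3 + 2 = 3 |
| 6 v 3 | 6 − 3 + 2 = 5 |
| 8 v 4 | 8 − 4 + 2 = 6 |
| 8 v 2 | 8 − 2 + 2 = 8 |
| 8 v 1 | 8 − 1 + 2 = 9 |
| 10 v 3 | 10 − 3 + 2 = 9 |

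Taking one report per intervention session as a yardstick (8 per person; the documents set no cap), the first four rows are within reach and the last two are not. The larger the gap between arms, the harder it is for one person to reverse it.

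**Step 2: an example.** Arm A has 6 participants with one flare each. Arm B has 3, one of whom reports a flare at all 8 sessions and two of whom report one each. Events: A 6, B 8 + 1 + 1 = 10. Participants: A 6/20 = 30% (exact 95% CI 11.9-54.3%), B 3/20 = 15% (3.2-37.9%). The intervals are Clopper-Pearson. They overlap widely, and Fisher's exact test gives p = 0.45, so the participant counts do not separate the arms either. What they add is a risk per person with its uncertainty.

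**Step 3: how often?** In a simulation of 50,000 trials with 20 per arm, each affected participant had a 10%, 20% or 30% chance of being a repeat flarer with 1 + Binomial(7, 0.6) events; the others had one event.

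| True participant risk | Trials in which events and participants point in opposite directions |
|---|---|
| 30% v 15% | 9.3-11.6% |
| 40% v 20% | 9.5-11.3% |
| 30% v 30% | 15.3-17.7% |

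With no repeat flarers the figure is 0% in every row. At a 30% risk, the variance-to-mean ratio of events per participant rises from 0.7 without repeats to 2.2-3.4 with them. This measures how far a few people come to drive the total.

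**The case against.** The strongest reply is that no analysis is harmed. Safety is descriptive, the feasibility outcomes are recruitment, attendance and retention, and there is no safety test, threshold or progression rule. Section 7 does not even say that safety will be tabulated by arm. A reader might infer that one participant could overturn the trial's safety comparison. The documents do not support that, because they plan no such comparison. Only an informal reading of the two arms is exposed.

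The mechanism also depends on a counting rule that the documents do not give. Section 8a lets the AE form be completed further as an event unfolds, which is compatible with one record for one continuing problem. Section 8 defines worsening against the pre-intervention period, not against the previous session. A reader might infer that pain flares will be the usual AE and that each will be logged anew at each session; neither is stated. This limits the claim, but it also shows that the planned event count is itself undefined until the rule is written down.

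Three further points stand. Counting participants reduces the dependence on how often people are asked but does not remove it, since more asking also raises the chance of at least one report. Both arms have the same 8 scheduled sessions, and no difference in asking is shown. With no events at all, 0/20 still allows a risk of up to 16.8% (1 − 0.025^(1/20)). That is a reason to give an interval, but it has nothing to do with recurrence. Finally, repeated flares in one person are a tolerability signal in their own right, so the event count should not be dropped.

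That the team could report participants anyway is true, since the forms are kept per participant. The plan does not commit to it, however, and leaving the choice until the data are seen allows selection between two summaries that can disagree.

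**Conclusion.** The point holds as a modest gap in descriptive reporting. As written, section 7 yields an event total that a few repeat reporters could dominate, and it yields no risk per participant. If flares are logged separately, a reading of the arms by events can differ from one by participants. With one event for everyone else affected, 3 to 8 events from one person are enough when the gap between arms is between 4 v 3 and 8 v 2. Under the assumed repeat-flare shares, discordance occurs in about 9-18% of trials. It disappears if nobody has repeat events or if recurrences are recorded as one AE. These figures rest on assumed AE frequencies and on 20 per arm. Nothing here invalidates a planned result. It is a cheap improvement.

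**What to change.** In section 7, state that safety will be reported by arm as the number and percentage of randomised participants with at least one AE, at least one AE related to the study and at least one serious AE, each with an exact (Clopper-Pearson) 95% confidence interval, alongside the number of events. Add one sentence saying whether a recurrence of the same symptom in the same person is counted as one AE or several, and have the AE form completed to match.

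The cost is a few lines of SAP text and a few extra table rows. The data are already to be collected, because forms are opened per participant and the PI assigns attribution. The intervals will be wide at about 20 per arm, which is an honest statement of what the trial can show. Keep the event count beside the participant count so that recurrence within a person stays visible.

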CAMS-R = Cognitive and Affective Mindfulness Scale – revised

MOOES = Modified Outcomes of Exercise Expectations Questionnaire

PGA-OA = Patient Global Assessment of Osteoarthritis

FABQ-PA = Fear Avoidance Beliefs about Physical Activity

CPSES = Chronic Pain Self-Efficacy Scale

PGIC = Patient Global Impression of Change

TUQ = Telehealth Usability Questionnaire

AE/SAE = Adverse Event/ Severe Adverse Event

 Table 2. Schedule of Optional In-Person Visit Procedures and Measurements

Week	-6 to -3	-2	-1	0	1	2	3	4	5	6	7	8
Visits			BV-I	RTT	Intervent	ion						W8-I
BMI, BP, and Wearable Sensors												
BMI Screening	X		X									
Height			X									X
Weight			X									X
Blood Pressure			X									X
Placement of lumbar-worn sensor for physical activity			X									X
3-sensor IMU system			X									X
Knee OA physical examination			X									X
Functional Tests												
7-meter walk test			X									X
Five-times-sit-to-stand test			X									X
6MWT			X									X
SCT			X									X
Strength Tests												
Knee Isometric Extension			X									X
Knee Isometric Flexion			X									X
Quantitative Sensory Testing												
QST (PPT, TS, CPM)			X									X
ЕІН			X									X
Brain Function Testing (fNIRS)												

Baseline (Resting)	X			X
Serial 7	X			X
Normal Walking	X			X
Dual-task Walking	X			X
Step-up	X			X
Sub-maximal isometric knee extension exercise	X			X
Electromyography	X			X

BV-I: Optional In-person Baseline Visit

RTT: Remote Randomization and Telehealth Training Visit

W8-I: Optional In-person Post-intervention Visit

BMI = Body Mass Index

BP = Blood Pressure

IMU = Inertial Measurement Unit

6MWT = 6-meter walk test

SCT = Stair Climb Test

QST = Quantitative Sensory Testing

PPT = Pressure Pain Threshold

TS = Temporal Summation

CPM = Conditioned Pain Modulation

EIH = Exercise-Induced Hypoalgesia

3. Recruitment and Eligibility

3a. Recruitment Strategies

Participants will be recruited through multiple channels. We will use TrialFacts (https://trialfacts.com/) for data-driven recruitment via social media. Trialfacts will prepare a study site, online pre-screening form, and recruitment material for social media. Other recruitment strategies will include:

- Flyers: IRB approved flyers will be placed at various approved locations on BU/BUMC campuses, primary care practices, senior centers, and other places where potential participants might congregate
- Online advertisements (e.g., Craigslist, Lab website, etc.)

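### The between-group PRO differences in Section 7 are adjusted for neither the baseline value nor sex, though both are available, and the wording fits two different unadjusted estimators

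*Combined protocol and SAP*

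**What the plan says.** Section 7 gives the PRO comparison one sentence: "For other PROs, within group changes and differences between groups along with 95% confidence intervals will be reported". No estimator, model, covariate or time point is named there or elsewhere in the document. On the analysis set it adds: "Data will be reported using an intention-to-treat approach with data from all randomized participants included. Missing data will not imputed".

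The data for an adjusted analysis are already planned:

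- **Baseline.** The study overview plans surveys of pain, function and mood before treatment, at week 8 and at week 14. Section 4a lists fifteen baseline surveys.
- **Follow-up.** Section 4d repeats baseline measures at week 8 and adds feedback and satisfaction surveys. At week 14, under section 4e, "participants will be administered six surveys related to their knee pain, function, perceived impression of change, and psychological measures".
- **Sex.** Section 4c states: "A randomization list will be generated by study biostatistician and will be stratified by sex". Separate envelope series are used for men and women, so sex is known for everyone randomised.

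**The concern.** A published difference with a 95% CI needs a defined estimator. The sentence in Section 7 fits a difference in mean change or a difference in mean follow-up value. In a trial of 40 these can give clearly different answers from the same data, and the choice would be left open until the results are known. Neither reading makes the best use of the baseline value: one subtracts it in full and the other ignores it. Sex determines the randomisation strata but has no place in the comparison. At stake is how stable and how precise the PRO estimates are, since readers may use them to judge whether a larger trial is worthwhile.

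**Working it through.** **Inputs from the document.** 40 are randomised (section 5b) with an equal chance of either arm (section 4c), so n = 20 per arm. Intervals are 95%, read as two-sided. The document gives no PRO standard deviation, effect size, expected dropout or power calculation, so there is no stated figure to reproduce.

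**Assumptions.** Results are in SD units, with equal variance at baseline and follow-up. The correlation r between baseline and follow-up is not given, so it is varied.

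**Step 1: how far apart the two unadjusted readings are.** With complete data, the difference in changes minus the difference in follow-up means equals minus the baseline difference between arms. That baseline difference has:

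- SD = sqrt(2/20) = 0.316
- mean absolute value = 0.316 × sqrt(2/π) = 0.252
- P(absolute value > 0.5) = P(|Z| > 0.5/0.316 = 1.58) = 0.114

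An imbalance above 0.3 SD occurs in about 34% of trials. At r = 0.5, an imbalance of 0.3 SD moves the follow-up difference by 0.3 × 0.5 = +0.15 SD and the change difference by 0.3 × (0.5 − 1) = −0.15 SD.

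**Step 2: standard errors.**

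- Follow-up means: sqrt(2/n)
- Change: sqrt(2/n) × sqrt(2(1 − r))
- ANCOVA on baseline: sqrt(2/n) × sqrt(1 − r²) × sqrt(1 + 1/(2n − 4))

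The last column was simulated (40,000 trials per setting, no true effect, sex not prognostic).

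| r | Change | Follow-up | ANCOVA, baseline only | Simulated: change / follow-up / adjusted for baseline and sex |
|---|---|---|---|---|
| 0.3 | 0.374 | 0.316 | 0.306 | 0.375 / 0.319 / 0.311 |
| 0.5 | 0.316 | 0.316 | 0.278 | 0.316 / 0.315 / 0.281 |
| 0.7 | 0.245 | 0.316 | 0.229 | 0.245 / 0.315 / 0.232 |

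At r = 0.5 the 95% half-width falls from 2.024 × 0.316 = 0.64 to 2.028 × 0.281 = 0.57 SD. An unadjusted analysis would need about 40 × (0.316/0.281)² ≈ 51 participants to match that.

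**Step 3: with 20% lost at random in both arms** (an assumed rate), the simulated SEs in the same order are 0.422/0.356/0.353 at r = 0.3, 0.357/0.355/0.320 at r = 0.5 and 0.274/0.356/0.262 at r = 0.7. Over Steps 2 and 3 together:

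- Gain over the better unadjusted option: from 1 − 0.353/0.356 ≈ 1% to 1 − 0.281/0.315 ≈ 11%.
- Gain over the worse: from 1 − 0.320/0.357 ≈ 10% to 1 − 0.262/0.356 ≈ 26%.

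**Step 4: when baseline predicts little.** At r = 0 the ANCOVA formula gives 0.316 × sqrt(1 + 1/36) = 0.321 against 0.316 for follow-up means, a cost of 1.4%. At r = 0.1 it gives 0.319, a cost of 0.9%. Simulation gave 0.321 against 0.316, and 0.318 against 0.315.

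**Step 5: the effect of sex.** With sex balanced by stratification and not prognostic, adding it changed the ANCOVA half-width by about 0.001 SD.

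**The case against.** The strongest reply is that the defect is ambiguity, and naming any estimator would cure it. Choosing ANCOVA is then a preference for efficiency worth only 1-11% over the better unadjusted option. For pain, r may be low, because section 3b requires a score of at least 4 at entry and that restricts the range. Adding sex brings no demonstrated precision. The trial is about feasibility and acceptability, and it has no PRO hypothesis test.

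Much of this stands, and it sets the priority. But r is unknown in advance, so the sponsor cannot tell which unadjusted option is the better one. Adjustment avoids that guess for a cost of about 1-2% in the worst case. Sex is included to match the stratified randomisation, not for a claimed gain.

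A reader might infer four stronger points that the document does not support:

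- **That Section 7 ignores baseline altogether.** It does not. Changes use baseline by subtraction, and a difference in changes is one permitted reading. What is absent is adjustment of the between-group difference.
- **That intention-to-treat contradicts no imputation.** Including everyone cannot hold literally for a change score once a follow-up value is missing. The natural reading, though, is available data by assigned arm, so this is a matter of wording.
- **That ANCOVA protects against dropout bias.** It does not in general. In simulations with an assumed 26% non-random loss in one arm and 10% random loss in the other, dropout depending on the week 8 value gave bias of up to 0.264 SD for ANCOVA and 0.203 SD for the change score. Nor can ANCOVA recover people who have no follow-up value.
- **That the main conclusions are at risk.** Recruitment, attendance and retention are descriptive and do not depend on the PRO estimator.

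**Conclusion.** The point holds as an inexpensive improvement of low to moderate priority. Section 7 leaves the PRO between-group difference open to two readings that differ by 0.25 SD on average, and it leaves out two covariates already in hand. The size of that gap rests only on 20 per arm, complete data and equal SDs. The precision gain also rests on the assumed r of 0.3 to 0.7. Near r = 0 it becomes a small loss. The benefit is a prespecified and usually tighter secondary estimate, and nothing more should be claimed for it.

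**What to change.** Replace the PRO and missing-data sentences in Section 7 with:

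> PROs are analysed by assigned arm on all observed data, without imputation. For PROs measured at baseline, the between-group difference and 95% CI at each follow-up visit (week 8, and week 14 where collected) are estimated by ANCOVA adjusted for the baseline value and sex. PROs with no baseline value are compared between arms adjusted for sex. Numbers contributing are reported per arm and visit.

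The second rule is needed because ratings such as impression of change and satisfaction exist only after treatment. Within-arm changes can still be shown descriptively.

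The cost is a short SAP edit and a standard model on data already planned, with no new visit, measure or participant. There are two drawbacks: a 1-2% larger SE if baseline turns out to be barely predictive, and possibly more bias than the change score if dropout depends on the unobserved outcome. Reporting the numbers contributing lets readers see how much is missing in each arm, although it does not correct for it.
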